### **6.5 Visit 2**

Participants will repeat all measures from Visit 1 at this study visit on their first thyroid preparation (LT4 or LT3). Subjects will stop taking study drug for 4 weeks after the study visit 2. During this wash-out period once every two weeks a phone contact will continue to be made by one of the study team members to inquire if the participant has experienced any adverse events. Specifically, the participant will be asked if they have any symptoms

CONFIDENTIAL

This material is the property of the University of Pennsylvania. Do not disclose or use except as authorized in writing by the study sponsor

of palpitations or shortness of breath. A six week supply of crossover study drug will either be sent home with the participant from study visit 2 or it will be mailed to them. Subjects will be instructed to begin this study drug 4 weeks after study visit 2. TSH level will be checked 4 weeks after starting the new study drug, and all study procedures for medication titration and TSH checks will be repeated as above.

## **6.6 Visit 3**

Participants will repeat all measures from Visit 2 at this final study visit on their second thyroid preparation (LT4 or LT3). The study will be complete.

## **6.7 Phone Contacts**

Once during the first week, a phone contact will be made by one of the study team members to inquire if the participant has experienced any adverse events following LT4 or LT3 supplementation. Thereafter, once every two weeks a phone contact will be made by one of the study team members to inquire if the participant has experienced any adverse events following drug supplementation. Specifically, the participant will be asked if they have any symptoms of palpitations or shortness of breath. Additionally, one day following each TRH administration (study Visits 1, 2, and 3) a phone contact will be made by one of the study team members to inquire if the participant has experienced any adverse events following study drug injection. If the participant experiences any adverse events following the final phone contact, they will have an emergency phone number to contact, which is [contact] as noted on the front of the informed consent document and utilized throughout the entire study.

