#### **LT4 and LT3:**

LT4 and LT3 have each been in therapeutic use for more than 50 years. Adverse reactions to either drug are exclusively related to excessive thyroid hormone, which can produce iatrogenic thyrotoxicosis. No serious adverse events were reported in a

CONFIDENTIAL

This material is the property of the University of Pennsylvania. Do not disclose or use except as authorized in writing by the study sponsor

published LT4/LT3 crossover study, and no symptoms of hyperthyroidism or hypothyroidism were reported.[25, 28] Participants will be asked about hyperthyroid symptoms, and a TSH level will be checked prior to the planned date if a patient reports any hyperthyroid symptoms.

Administration and monitoring of LT4 and LT3 will be modeled off of a published protocol.[28] The dosing of thyroid hormone will be based on published studies of thyroid hormone replacement in subclinical hypothyroidism. The literature supports a 1 mcg/kg/day dose for initiation of therapy.[29-34] We will tailor the thyroid hormone dose to each subject using a weight-based dosing scheme that is also based on how far the subject's TSH level is from goal. The dosing scheme is conservative. 1mcg/kg is the dose reported in the literature. The initial dose in our study will be lower than that - 0.7mcg/kg/day given that we are studying subjects 70 years and older. We will use thrice daily dosing due to the short half-life of LT3.

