## **6.2 Visit 1 (Day 1)**

Participants will arrive at 7:30 am after a 12-hour fast. Weight and vital signs including heart rate, rectal temperature, and blood pressure will be measured. The activity and heart rate monitors will be collected. An REE evaluation by indirect calorimetry will be completed.

An IV will be inserted into the forearm and blood will be collected at times -5 and 0, followed by injection of 200 µg TRH.[28] Additional blood will be collected at 5, 10, 15, 20, 30, 60, 120, and 180 minutes, immediately processed, and stored at -80 degrees for measures of TSH, free T4, and total T3 (all time points), prolactin, alpha subunit, reverse T3 (0, 60, and 180 minutes), and a lipid profile (time 0). Additional samples at the 0, 120, and 180 time points will be processed and saved for TSH bioactivity measurements and TSH structure evaluation. If the participant consents to the optional exploratory genetic research study, then a sample will be collected, processed and saved for genetic testing at one study visit only (time -5).

Blood pressure will be monitored before administration of TRH, and at 5, 15, 30, 60, 120, 180 minutes.

Questions about health status, quality of life, and hypothyroid symptoms will be completed. Digit symbol substitution test will be completed.

Participants will be provided with lunch and undergo a DXA scan.

Participants will then undergo arterial tonometry and Doppler echocardiography testing. Assessment of arterial load will be made from this data.

Arterial tonometry: We will use a commercially available system (SphygmoCor, AtCor Medical) that uses a high-fidelity applanation tonometer (Millar Instruments; Houston, TX). The tonometer will be used to record carotid, radial and femoral arterial pressure waveforms. Mean brachial pressure will be obtained from a radial waveform calibrated with brachial systolic and diastolic pressures, measured with a validated oscillometric device. Diastolic and mean pressures will then be used to calibrate the carotid pressure waveform. Carotid-femoral and carotid-radial pulse wave velocity (PWV) will be computed from the time delay between the waveform foot on these arterial sites and the distance between the sites (measured on the body surface), where PWV = distance/time.

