### **6.4 Medication Titration (Q4Weeks)**

Participants will have TSH testing every 4 weeks (acceptable range 4-8 weeks) at a Penn outpatient laboratory facility until TSH is at goal, and then the participant will be scheduled for Visit 2. This visit can be scheduled up to four weeks from the date of the last TSH level.

Symptoms of palpitations and shortness of breath will be ascertained at the reminder calls prior to TSH level checks. The total daily dose of study medications will be adjusted by blinded study investigators to a TSH of 0.5-1.5 mU/L. New study medication for adjustment dosing will be mailed overnight to participants within 5 days of receipt of the interim lab results. Once the TSH is at goal, an activity and heart rate monitor will be mailed to the participant to wear one week prior to the next study visit.

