### **Adverse Event**

An **adverse event** (AE) is any symptom, sign, illness or experience that develops or worsens in severity during the course of the study. Intercurrent illnesses or injuries should be regarded as adverse events. Abnormal results of diagnostic procedures are considered to be adverse events if the abnormality:

- results in study withdrawal
- is associated with a serious adverse event
- is associated with clinical signs or symptoms
- leads to additional treatment or to further diagnostic tests
- is considered by the investigator to be of clinical significance

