#### Hyperthyroid Symptoms assessed with each telephone encounter while on study drug:

1. palpitations

CONFIDENTIAL

This material is the property of the University of Pennsylvania. Do not disclose or use except as authorized in writing by the study sponsor

2. shortness of breath

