**Hyperthyroid Symptoms assessed at each study visit:**

1. anxiety
2. irritability
3. muscle discomfort or weakness
4. tremor
5. heat intolerance
6. palpitations
7. fatigue
8. weight loss
9. frequent bowel movements
10. shortness of breath

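### During titration, calls name only 2 of the 10 listed hyperthyroid symptoms, so structured questions only partly feed the early-TSH safeguard in section 1.5

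*Combined protocol and SAP*

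**What the plan says.** Section 1.5 attributes all adverse reactions to LT4 and LT3 to an excess of thyroid hormone and sets a safeguard: "a TSH level will be checked prior to the planned date if a patient reports any hyperthyroid symptoms".

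Appendix 1 gives two lists. The one headed "Hyperthyroid Symptoms assessed at each study visit" has ten items. The one headed "Hyperthyroid Symptoms assessed with each telephone encounter while on study drug" has two, palpitations and shortness of breath. Sections 3.4, 6.4, 6.5 and 6.7 all name that same pair for telephone contacts; the wording in 6.7 is "Specifically, the participant will be asked if they have any symptoms of palpitations or shortness of breath".

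The calls in 6.7 also carry a general enquiry about adverse events. After one call in the first week, it recurs: "once every two weeks a phone contact will be made by one of the study team members to inquire if the participant has experienced any" such event. Section 8.1 defines an adverse event broadly, as one that "is any symptom, sign, illness or experience that develops or worsens in severity during the course of the study", and section 8.2 requires enquiry about adverse events at every contact.

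On timing, section 3.1 starts dosing on the morning after Visit 1. Section 6.4 continues TSH testing "until TSH is at goal, and then the participant will be scheduled for Visit 2". Sections 3.1 and 6.5 repeat that sequence for the second preparation and Visit 3. For the questionnaires at Visit 1, section 6.2 says "Questions about health status, quality of life, and hypothyroid symptoms will be completed" and does not mention hyperthyroid symptoms.

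**The concern.** The safeguard in 1.5 is worded for any hyperthyroid symptom, but the plan's systematic questions during titration are narrower. Titration is the phase in which the dose is still moving and TSH may fall below target. The plan allows for this, since its dosing tables have reduction columns for TSH of 0.20-0.49 and below 0.20. The full list is asked when excess hormone is least expected: before any drug, or after a TSH within 0.5-1.5 mU/L.

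Two things are at stake. One is how reliably a symptom between TSH checks leads to the early check that 1.5 promises. The other is the symptom data. For most of the list there will be no structured record from the titration phase, so the trial can say little about how often those symptoms occurred while doses were being adjusted.

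**Working it through.** The plan states no figure on this point, and the sample-size calculation does not bear on it. The check is a count and a comparison of sections.

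**1. Overlap of the two Appendix 1 lists.** Visit list: 10 items. Call list: 2 items, both also on the visit list. Not named on calls: 10 − 2 = 8. These are tremor, anxiety, irritability, heat intolerance, fatigue, weight loss, muscle discomfort or weakness, and frequent bowel movements.

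**2. Where each list falls in relation to drug and TSH.**

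| Contact | Timing | Hyperthyroid symptoms named |
|---|---|---|
| Visit 1 (3.1, 6.2) | Before the first dose | 10 (Appendix 1) |
| First-week and two-weekly calls (3.4, 6.7) | On drug, including titration | 2, plus general adverse-event question |
| Reminder calls before TSH tests (6.4) | Titration | 2 |
| Visit 2 (3.1, 6.4) | After an at-goal TSH, up to four weeks later | 10 (Appendix 1) |
| Wash-out calls (6.5) | Off drug | 2, plus general adverse-event question |
| Visit 3 (3.1, 6.5, 6.6) | After an at-goal TSH on the second drug | 10 (Appendix 1) |

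No study visit falls inside either titration phase, so the ten-item list is not asked there.

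**3. Length of the interval concerned.** Section 6.4 sets TSH tests 4 weeks apart and accepts 4 to 8. With a call every two weeks, that is about 4/2 = 2 to 8/2 = 4 routine calls per interval, plus the reminder call, each naming two symptoms. After crossover, sections 1.5 and 5.2 start the second drug at the dose equivalent to that at Visit 2. They plan no TSH at the end of wash-out and set the first check 4 weeks after starting. Within these intervals, symptom reports are the only signal that could bring a TSH check forward.

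**4. How the other eight symptoms can reach the safeguard.** They can be raised in answer to the general question in 6.7, or through the emergency telephone number that 6.7 makes available throughout. Section 8.2 asks for specific questioning, but the only specific symptom questions written for calls are the two. The early-TSH provision appears in 1.5 and is not repeated in 6.4, 6.7 or Appendix 1. No section says that an adverse-event report of, for example, tremor leads to that check.

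**5. Section 6.2 against Appendix 1.** Visits 2 and 3 repeat the Visit 1 measures (6.5, 6.6), and 6.2 names hypothyroid symptoms only. That the ten items are asked at visits rests on Appendix 1 and the pointer to it in 3.4.

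**The case against.** The strongest reply is that overtreatment is detected mainly by TSH. Tests are scheduled every 4 weeks (4 to 8 accepted), results come back in under 24 hours (6.8), and the dosing tables provide reductions. Titration also has a first-week call, two-weekly calls and reminder calls. The two-tier symptom list is used consistently in 3.4, 6.4, 6.5 and 6.7, so it looks deliberate. All of this stands, and it confines the point to the time between checks.

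A reader might infer that the safeguard receives no input during titration. The documents do not support that. The condition in 1.5 is a report and does not require a prompted item. Two listed symptoms are asked at least every two weeks, and the other eight can be volunteered.

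A reader might also infer that the safety endpoint in 3.4 is measured only in people whose TSH is in range. It is not: 3.4 includes palpitations and shortness of breath by telephone every two weeks on drug, and adverse events are recorded throughout. Comparing baseline with each preparation at target TSH is also the stated intent of the symptom objective in section 2. Only the structured data on the remaining eight symptoms are limited to visits.

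Finally, a reader might try to size the gap from the LT4 table: 0.25/0.09 = 2.8, so three reductions to undo one increase, or 12 weeks at 4-week checks and 24 at 8-week checks. That does not measure a detection gap. The first reduction comes only after a low TSH is already known. The +0.25 step applies only at TSH above 4.50, so undoing it in full would return the participant to a dose at which TSH was above goal.

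The mismatch in 6.2 is small in a single-centre trial in which 3.4 points to Appendix 1. It is a missing cross-reference.

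**Conclusion.** The point holds as a modest, inexpensive improvement. During titration, 2 of the 10 listed hyperthyroid symptoms are asked about by name, and 8 of 10 rely on open reporting between scheduled TSH checks. For those eight, structured on-drug data come only after TSH has reached goal. The early-TSH provision is worded more widely than the call questions that would feed it, and the sections that govern calls and titration do not repeat it.

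This rests on reading Appendix 1 literally, with ten items at visits and two on calls, and on there being no fuller call script outside the documents. The documents do not show how many participants would have an unprompted symptom go unreported, so no rate of missed events is claimed. The conclusion does not depend on any view of the correct dose or the correct response to a symptom.

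**What to change.** - Collect the existing ten-item Appendix 1 list at the telephone contacts already scheduled on drug, and change the call list in Appendix 1 and the wording in 3.4, 6.4 and 6.7 to match.
- Name the hyperthyroid list in 6.2, so that the visit procedures agree with Appendix 1 and 3.4 and the pre-drug answers are plainly required.
- Reconcile 1.5, 6.4, 6.7 and Appendix 1 on which symptom reports lead to the early TSH that 1.5 already promises. The content of that rule is for the sponsor; none is proposed here.

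The cost is a change of call script and slightly longer calls. Some unscheduled TSH checks will be negative, because several items are non-specific; fatigue, for instance, stands on both the hyperthyroid list in Appendix 1 and the hypothyroid list in Appendix 2. No visit, dose or sample-size change is needed.

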## **6.8 Assays**

All screening blood assays will be performed at William Pepper Laboratory, and will include a CBC, TSH, FT4, TPO antibodies, and a complete metabolic panel including liver function tests to exclude hyperglycemia, renal insufficiency, or hepatic insufficiency. Total blood volume drawn at the screening visit is approximately 12 ml. This will be drawn as two gold-serum separator tubes and one lavender-top tube each containing 4 ml of blood. If a hemoglobin A1C level has not been checked on diabetic participants in the last 6 months, a hemoglobin A1C level will be added on to the screening labs.

During the baseline study visit and study visit on each treatment arm, blood will be collected and batched for biochemical assays for TSH, free T4, total T3, prolactin, and a lipid profile, to be performed by the Pepper laboratory. Reverse T3 and alpha-subunit will be measured using available kits. TSH bioactivity will be measured under the guidance of [name] laboratory at NIDDK. A sample for genetic testing will be collected at one study visit if the participant consents to the optional genetic research study. At the completion of the subject participation portion of the study, the optional genetic specimens, de-identified, will be sent to [name] at Virginia Commonwealth University for analysis. When complete, the samples and analysis will be sent back to Penn for incorporation into the study database.

Total blood volume drawn at each study visit is approximately <90 mL. Total blood drawn at these three visits combined is approximately <270 mL.

CONFIDENTIAL

This material is the property of the University of Pennsylvania. Do not disclose or use except as authorized in writing by the study sponsor

For interim thyroid hormone titration, a TSH level will be performed every 4 weeks until TSH is at goal. These TSH levels have a turnaround time of <24 hours. Total blood drawn at each titration draw is approximately 4 mL and will not cumulatively exceed 52 mL.

## 7 Statistical Plan

### 7.1 Sample Size Determination

We plan to enroll 30 subjects with an anticipated 15% dropout rate. With an alpha of 0.05 and 80% power and 15% dropout, we will be able to detect a 0.58 standard deviation (SD) change in outcome from baseline. A 3 SD improvement in unstimulated TSH bioactivity has been reported after treatment of overt primary hypothyroidism.[4] No previous studies have measured TSH bioactivity in subclinical hypothyroidism.

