## Study Summary

Title	The Thyroid Axis in Older Individuals with Persistent Subclinical Hypothyroidism: a Mechanistic, Randomized, Double-Blind, Cross-Over Study of Levothyroxine (LT4) and Liothyronine (LT3) Administration
Short Title	LT4 and LT3 in Subclinical Hypothyroidism
Protocol Number	821564
Phase	
Methodology	Randomized, Double-Blind, Cross-Over Study
Study Duration	Three years
Study Center(s)	Single-center
Objectives	To examine the pituitary-thyroid axis in older individuals with persistent subclinical hypothyroidism utilizing dynamic testing with thyrotropin releasing hormone (TRH) stimulation under different therapeutic conditions of either LT4 or LT3. We will measure thyroid stimulating hormone (TSH) area under the curve (AUC), $TSH_{max}$ , change in TSH bioactivity, and change in free T4 and total T3 levels. All outcomes will be assessed at baseline and after achieving target TSH levels with each thyroid preparation.
Number of Subjects	Thirty
Diagnosis and Main Inclusion Criteria	Men and women aged 70 and older with persistent subclinical hypothyroidism
Study Dose, Regimen	Product, Route, 1. Intravenous TRH 200 µg at study visit 1 (baseline), study visit 2 (on first thyroid treatment), and study visit 3 (on second thyroid treatment) 2. Oral LT4 with a total starting dose of 0.7mcg/kg/day split into three daily doses and titrated to a target TSH level of 0.5 -1.5mU/L 3. Oral LT3 with a starting dose of 1/3 of the weight based LT4 dose divided into three daily doses titrated to a target TSH level of 0.5 -1.5mU/L
Duration administration	of 1. Three single administrations of TRH (at baseline study visit 1, study visit 2 on the first thyroid treatment, and study visit 3 on the second thyroid treatment) 2. LT4 taken as divided doses three times daily 3. LT3 taken as divided doses three times daily 4. For LT4 and LT3, there will be medication adjustments every four weeks as needed until the TSH level is at goal.

CONFIDENTIAL

This material is the property of the University of Pennsylvania. Do not disclose or use except as authorized in writing by the study sponsor

Reference therapy	None
Statistical Methodology	Changes in TRH stimulation test parameters and other outcomes will be compared from baseline for each thyroid hormone preparation (LT4 or LT3) via paired t-tests and between treatment arms via two-tailed tests. AUC for TRH stimulated TSH response will be calculated. Nonparametric tests will be employed as needed.

CONFIDENTIAL

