## 2 Study Objectives

To understand the function of the thyroid axis in subclinical hypothyroidism, by examining the thyroid axis in older individuals with persistent subclinical hypothyroidism under dynamic conditions.

Primary Objective:

CONFIDENTIAL

This material is the property of the University of Pennsylvania. Do not disclose or use except as authorized in writing by the study sponsor

To assess the adaptability of the thyroid axis to perturbations from TRH stimulation or thyroid hormone supplementation via assessment of TRH stimulation test parameters (TSH AUC, TSHmax, change in TSH bioactivity, change in free T4, change in total T3) at baseline and after achieving target TSH levels with each thyroid preparation.

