### **3.2 Primary Study Endpoints**

Changes in TRH stimulation test parameters (listed below) will be measured at each study visit:

1. TSH area under the curve (AUC)
2. TSHmax
3. Free T4
4. Total T3
5. TSH bioactivity measured by an *in-vitro* cell-based bioactivity assay [35]

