## 4 Subject Selection and Withdrawal

### 4.1 Inclusion Criteria

We will include men and women aged 70 and older who are able to provide informed consent and have a TSH between 4.5 and 19.9 mU/L in conjunction with a normal free thyroxine (FT4) level.

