### 7.2 Statistical Methods

All statistical analyses will be performed under consultation with [name], Ph.D., a CTRC biostatistician. Our primary goal will be to assess changes in TRH stimulation test parameters at baseline compared to each thyroid hormone supplementation (LT4 or LT3) and our secondary goal will be to compare physiologic responses to LT4 and LT3 therapy from baseline. The area under the curve (AUC) for TRH-stimulated TSH response will be calculated using the trapezoidal rule. The maximum serum TSH concentration following TRH administration ( $TSH_{max}$ ) will be obtained by direct inspection of the serum concentration-time profiles. Changes in TSH bioactivity, free T4, and total T3 will be determined using the higher of the 120 or 180 minute post-TRH values. Paired t-tests will be used to examine change from baseline for each preparation, and two-tailed tests will be used to compare data between treatment arms. Nonparametric tests will be employed as needed. The primary outcomes will be the changes in TRH stimulation test parameters (AUC,  $TSH_{max}$ ,  $\Delta$  TSH bioactivity,  $\Delta$  free T4,  $\Delta$  total T3). Additional outcomes will include changes in unstimulated TSH bioactivity, REE, body temperature, weight, body composition, lipids, physical actigraphy and heart rate, cognitive testing, symptoms, arterial tonometry, and Doppler echocardiography.

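### Do ten unranked, unadjusted primary comparisons resting on one 0.58 SD power statement call for a change to the plan?

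*Combined protocol and SAP*

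**What the plan says.** Sections 2, 3.2 and 7.2 list the same five primary outcomes without ranking them: TSH AUC, TSHmax, and the changes in TSH bioactivity, free T4 and total T3 after TRH. Section 3.2 introduces them with "Changes in TRH stimulation test parameters (listed below) will be measured at each study visit".

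Section 7.2 puts the primary aim this way: "Our primary goal will be to assess changes in TRH stimulation test parameters at baseline compared to each thyroid hormone supplementation (LT4 or LT3"). The test is also given there: "Paired t-tests will be used to examine change from baseline for each preparation". The same section adds that "two-tailed tests will be used to compare data between treatment arms", and the Study Summary has the matching line, "for each thyroid hormone preparation (LT4 or LT3) via paired t-tests and between treatment arms via two-tailed tests".

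Section 7.1 has one power statement: "With an alpha of 0.05 and 80% power and 15% dropout, we will be able to detect a 0.58 standard deviation (SD) change". It refers to outcome in general and names neither a parameter nor a preparation. The only published effect it cites, 3 SD, is for unstimulated TSH bioactivity, which Sections 3.3 and 7.2 place outside the primary set.

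Nowhere does the plan rank the tests, adjust for multiplicity, define success, or say that the tests are exploratory or per comparison.

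**The concern.** Five outcomes on two preparations give ten results that all carry the word primary, beside one alpha of 0.05. A reader meeting this for the first time would ask which result the trial rests on, and what one p-value below 0.05 would support. With ten chances, some spurious significance is quite likely, and a report could stress whichever result came out well without departing from the protocol.

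The power statement adds to the unease. If 0.05 were meant for the whole family, 0.58 SD would be too optimistic and 30 participants would be too few for that effect. The between-arm tests, which have no stated rank, seem to enlarge the family further.

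**Working it through.** **Inputs.** 30 enrolled, 15% dropout, alpha 0.05, power 80%, 0.58 SD (Section 7.1). Five outcomes, two preparations, paired t-tests (Section 7.2). Completers: 30 × 0.85 = 25.5, so 25 or 26. A two-sided test is assumed for the paired comparisons, because the plan says two-tailed only for the between-arm ones.

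**1. The plan's own figure.** For a paired test on n within-person changes with true mean change δ (in SDs of the change), power = P(|T| > t(1−α/2, n−1)), where T is noncentral t with n−1 degrees of freedom and noncentrality δ√n. Solving for 80% at α = 0.05:

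- n = 25: critical value 2.064, δ = 0.584
- n = 26: critical value 2.060, δ = 0.572
- n = 25.5: δ = 0.578

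Other readings miss 0.58. The normal approximation gives (1.960 + 0.842)/√25 = 0.560, a one-sided t-test 0.512 (n = 25), no dropout 0.529 (n = 30), and two groups of 13 about 1.10. Splitting alpha over ten tests gives 0.78-0.80 (step 4). So 7.1 describes one unadjusted two-sided paired test, and it applies equally to each of the ten.

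**2. Size of the family.** 5 × 2 = 10. The primary goal in 7.2 and the primary objective in Section 2 cover comparisons with baseline only, so the between-arm tests are not counted.

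Nor are all ten nulls equally plausible. Entry requires that participants "have a TSH between 4.5 and 19.9 mU/L in conjunction with a normal free thyroxine (FT4) level", and treatment is titrated to 0.5-1.5 mU/L (Section 3.1). Unstimulated TSH must therefore fall at least 4.5/1.5 = 3-fold from the entry value. AUC and TSHmax will probably fall with it, which leaves six tests in real doubt.

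**3. Chance of at least one false positive, each test at 0.05.** If independent, 1 − 0.95^k gives 9.75% (k = 2), 26.5% (k = 6) and 40.1% (k = 10). The tests are not independent, since both preparations share a baseline. With equal variances and a common between-visit correlation ρ, the two changes have covariance σ²(1−ρ) and variance 2σ²(1−ρ), hence correlation 0.5. The simulation used n = 25, normal changes and 40,000 runs. Each range runs from outcome correlation 0 to 0.9:

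| Tests | Correlation between preparations 0.5 | 0.7 | 0.9 |
|---|---|---|---|
| 2 (bioactivity) | 9.0% | 8.5% | 7.2% |
| 6 (bioactivity, free T4, total T3) | 24.8-15.4% | 23.3-13.8% | 19.5-11.9% |
| 10 | 37.8-18.2% | 35.7-17.2% | 30.6-14.5% |

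The plan gives no correlations, so all of these are assumed.

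**4. What control would cost.**

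| Alpha for one test | Detectable at 80% power (n = 25 / 26) | Power at 0.58 SD |
|---|---|---|
| 0.05 | 0.584 / 0.572 SD | 79.5% / 81.1% |
| 0.05/2 = 0.025 | 0.651 / 0.637 SD | 69.3% / 71.4% |
| 0.05/6 = 0.0083 | 0.751 / 0.734 SD | 52.1% / 54.5% |
| 0.05/10 = 0.005 | 0.796 / 0.777 SD | 44.3% / 46.8% |

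The 0.05/6 row is Holm's threshold once the four AUC and TSHmax tests have been rejected. Holding 0.58 SD at 80% power with alpha 0.005 needs 44 completers, or 44/0.85 = 51.8, so 52 enrolled.

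**5. What the unadjusted plan delivers.** The 95% confidence interval for each change has half-width t(0.975, n−1)/√n: 2.064/5 = 0.413 SD for n = 25, and 0.404 SD for n = 26.

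**The case for a change.** The strongest case for a change is that the word primary carries meaning. Five outcomes bear it, one alpha is attached, and a single sentence saying that the tests are per comparison would cost nothing. Even on the narrowest reading, with only the two bioactivity tests in doubt, the false-positive chance is 7-9% rather than 5%. Those tests address the study's central hypothesis, and without a stated rule, emphasis can be chosen after the results are known.

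Much of this stands. The wording gap is real, the count of ten is right, and the sentence would do no harm. But it would alter no test, sample size, detectable effect or estimate. It would record what 7.1 already implies, since 0.58 SD arises only per comparison.

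The remedies that would alter something are trade-offs. Holm takes power at 0.58 SD below one half at its strictest step. A single named outcome sets aside four of the five TRH-test parameters that Section 2 asks for together.

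Adding the between-arm tests to enlarge the family does not stand, because neither the primary goal nor the primary objective includes them.

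**Conclusion.** No change is needed. The 0.58 SD in 7.1 is correct for any one of the ten comparisons, and the plan makes no claim that it holds for the family. Unadjusted testing leaves a false-positive chance of about 7-9% for the two bioactivity tests, 12-25% for six and 15-38% for all ten. The ceilings under independence are 10%, 26% and 40%. That is acceptable for a mechanistic crossover study of 30 people whose objective is to describe how the thyroid axis responds, and which sets no success criterion.

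This rests on three assumptions: the paired tests are two-sided, 25 or 26 people contribute to each, and analysts report all ten changes with their intervals and rest no confirmatory claim on one p-value. Section 7.3 keeps anyone with data from baseline onward, so the number for one preparation could be slightly higher, which would only help. If a report later presented one significant result as proof of effect, the criticism would fall on that report's claim.
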